5.2 Analysis populations

Each subject's inclusion/exclusion status with regards to each analysis population will be assigned before breaking the blind.

5.2.1 Full analysis population

The full analysis population (FAP) consists of all randomized subjects, with the sole exception of subjects that were randomized by mistake and never included into the trial. Subjects with follow-up data, who were randomized but did not fulfil all eligibility criteria will

be included. Subjects who withdrew their written informed consent will be included until the date of consent withdrawal (see Section 4.9.7 for details).

5.2.2 Per protocol populations

The per protocol population at 3 years (PP3) consists of all subjects in the FAP who had at least 80 % compliance, fulfill all eligibility criteria, no significant protocol violations, and have either reached a study endpoint (recurrence, other cancer, or death) within 3 years, or completed at least 3 years in the trial.

The per protocol population at 5 years (PP5) consists of all subjects in the FAP who had at least 80 % compliance, no significant protocol violations, fulfill all eligibility criteria, and have either reached a study endpoint (recurrence, other cancer, or death) within 5 years, or completed at least 5 years in the trial.

Subjects who are thought to fulfil all eligibility criteria at randomization, but later are found not to fulfil all eligibility criteria will be excluded from the PP3 and PP5, for example subjects where Lynch syndrome is discovered after randomization.

Significant protocol violations include more than 12 weeks from surgery until randomization, leaving the study because of pregnancy, lack of compliance with the study protocol, wanting to leave the study, refusal to cooperate, other medical reasons, e.g. initiating another treatment not compatible with ASA, or leaving the trial because of an SAE/AE.

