Subjects leaving the trial for any reason between two clinic visits, or between the first phone contact and the succeeding clinic visit, will not have a compliance measurement for the time between the last clinic visit (or Visit 4) and trial exit. For these subjects, an assumption on how long C_{LCV} (or C_{V4}) is assumed valid must be made. Denote the last date for which C_{LCV} (or C_{V4}) is assumed valid $D_{LCV/V4}$. For subjects experiencing recurrence, death, or other cancer, $D_{LCV/V4}$ will be defined as the date of last IMP intake, if such a date is registered in the eCRF, or the event date (see Section 6.2.1 for definition), whichever comes first. For subjects leaving the trial before an endpoint or before trial completion, $D_{LCV/V4}$ will be defined as the date of last IMP intake, if such a date is registered in the eCRF, or the Visit 15 date/EoS date, whichever comes first. For subjects completing 3 years in the trial, $D_{LCV/V4}$ will be defined as the date of Visit 15 (the 3-year follow-up clinic visit). The number of days for which C_{LCV} (or C_{V4}) will be assumed valid will be calculated as days from randomization until $D_{LCV/V4}$, subtracting the number of days on treatment breaks (before $D_{LCV/V4}$) not allowed by the protocol (see above), for each randomized subject having received the IMP at least once.

For subjects reaching a trial endpoint, days from $D_{LCV/V4}$ until the event date will be defined as having 0 % compliance. Similarly, for subjects leaving the trial before completion, days from $D_{LCV/V4}$ until 3 years from randomization will be defined as having 0 % compliance. For all subjects, regardless of trial completion or exit, days on treatment breaks (before $D_{LCV/V4}$) not allowed by the study protocol will be defined as having 0 % compliance. Overall compliance (OC) will be calculated as a weighted average between C_{LCV} (or C_{V4}) and 0, as follows

OC % =
$$\frac{\text{Valid days*C}_{\text{LCV or V4}} + \text{Zero-compliance days*0}}{\text{Valid days+Zero-compliance days}}.$$

Subjects with an EoS event before the first phone contact will not have answered the question on frequency in taking the IMP, or have any pill counts in the eCRF, hence, it is not possible to calculate compliance for such subjects.

See 6.2.2 for derivation of the variables needed for compliance calculation.

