For the analyses on the PP3 and PP5 populations, stabilized inverse probability of treatment weights (IPTW) will be used to estimate the effect on the randomized population. The stabilized IPTW for each subject in the PP3 and PP5 populations will be calculated as the ratio between the probability of receiving the treatment that was received (ASA or Placebo) estimated from a logistic regression model without covariates, and the probability of receiving the treatment that was received (ASA or Placebo) estimated in a logistic regression model including the covariates age, sex, country, BMI, tumor location (colon/rectum), type of neoadjuvant treatment, ASA score, time from surgery until randomization, calendar time of randomization, platelet count at baseline, CEA at baseline, MSI status, BRAF V600E status, KRAS status, and tumor differentiation. The use of inverse probability of censoring weights (IPCW), in addition to the IPTW's, for the PP analyses has been considered, but deemed unsuitable for the ALASCCA trial data for several reasons: 1) The time-point for which a subject is to be considered non-compliant is not well-defined, and therefore an IPCW approach would demand strong assumptions and/or looking into the future for certain subjects, 2) Compliance (described in Section 4.8.2) is defined as a weighted average of the visit-specific compliance measurements over the whole study period, and censoring at the first visit-specific non-compliance would result in the censoring of a substantial number of subjects with an overall compliance of >80%, and 3) There are no relevant time-dependent covariates measured during follow-up to be included for capturing treatment-confounder feedback. Given the above considerations, the limitations of the suggested PP analysis approach must be highlighted when presenting the trial results.

A secondary or exploratory analysis involving the Mutation B subgroup may be subjected to sensitivity analysis to assess the impact of observations that may not represent true driver (cancer-relevant) variants. This may include repeating the analysis using a subset containing only high-confidence driver variants.

Table 10. Specification of variables and populations for the exploratory analyses in the ALASCCA trial for 3-year endpoints. Mutation A: PIK3CA exon 9 and 20 hotspot small mutations,

Mutation B: other PIK3CA, PIK3R1 and PTEN non-silent small mutations and focal/homozygous deletion of PTEN.

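### PP3/PP5 membership depends on the outcome, and weights that model arm only cannot carry the exploratory per-protocol hazard ratio back to the randomised population

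*SAP*

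**What the plan says.** SAP 5.2.2 builds PP3 from FAP subjects who are eligible, at least 80% compliant and without significant protocol violations, and who "have either reached a study endpoint (recurrence, other cancer, or death) within 3 years, or completed at least 3 years in the trial". PP5 members must "have either reached a study endpoint (recurrence, other cancer, or death) within 5 years, or completed at least 5 years in the trial". The list of significant violations covers most reasons for leaving, among them "or leaving the trial because of an SAE/AE".

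SAP 4.8.2 sets the compliance denominator according to outcome. For subjects with an endpoint, days after the last valid date "until the event date will be defined as having 0 % compliance". For those who leave before completion, such days "until 3 years from randomization will be defined as having 0 % compliance".

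SAP 8.3 says that "stabilized inverse probability of treatment weights (IPTW) will be used to estimate the effect on the randomized population". It continues: "The stabilized IPTW for each subject in the PP3 and PP5 populations will be calculated as the ratio", with a covariate-free model for arm in the numerator and a model for arm given baseline covariates in the denominator. No model for being in PP3 or PP5 is planned. Inverse probability of censoring weights (IPCW) are rejected for three reasons, and the limitations of the approach are to be highlighted.

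**The concern.** Selecting on the outcome distorts a time-to-event comparison even when leaving has nothing to do with prognosis. Among subjects who would leave at some point, those who recur first stay in the set. Those who leave first are removed, together with the event-free time that they contributed. Observed recurrence therefore rises in each arm, and rises more in the arm with more withdrawal. Leaving for an adverse event is one of the deletion reasons, so a difference between aspirin and placebo is possible.

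At stake are the interpretation of the exploratory per-protocol HR and the accuracy of the SAP's statement about the population it describes.

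**Working it through.** **Inputs.** From SAP 4.5.2: placebo 3-year recurrence 18%, RR 0.38, 10% drop-out with no split by arm, 135 per arm without drop-out and 150 with it. Assumed: withdrawal rates by arm, and constant hazards of recurrence and withdrawal. Leavers are treated as out of PP3. Compliance, other cancer and death are left out.

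**The plan's own figure.** With p1 = 0.18, p2 = 0.38 × 0.18 = 0.0684 and mean 0.1242, the two-proportion formula is n = [1.96·√(2·0.1242·0.8758) + 0.842·√(0.18·0.82 + 0.0684·0.9316)]² / 0.1116² = 136 per arm (stated 135; power at 135 is 79.7%). Then 135/0.9 = 150, as stated. The documents give no figure for the per-protocol HR.

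**Two subjects side by side.** One takes every tablet and recurs at month 6. Compliance is 100% to the event, so the subject is in PP3. Another takes every tablet and leaves event-free at month 6. Compliance is 6/36 = 17%, the 3 years are not completed, and the subject is deleted. With full adherence up to exit, a leaver must stay 0.8 × 36 = 28.8 months just to meet the 80% rule.

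**Closed form.** Recurrence hazard λ = −ln(0.82)/3 = 0.0662 per year. For 3-year withdrawal w, μ = −ln(1−w)/3. Then:
- kept with an event: E = λ/(λ+μ) · (1 − 0.82(1−w))
- kept as a completer: C = 0.82(1−w)
- PP3 risk R = E/(E+C), and cumulative hazard H = −ln(1−R)

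| w | E | C | R | H |
|---|---|---|---|---|
| 10% | 0.171 | 0.738 | 0.188 | 0.2086 |
| 20% | 0.162 | 0.656 | 0.198 | 0.2206 |
| 30% | 0.152 | 0.574 | 0.210 | 0.2353 |

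For w = 8%, 12% and 15%, H = 0.2064, 0.2108 and 0.2143. The ratio of H between arms approximates the PP3 HR when the true HR is 1. Simulated Cox HRs (800,000 per arm, with separate runs agreeing within about 0.01) confirm it:

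| Withdrawal ASA/placebo | Ratio of H | Simulated PP3 HR |
|---|---|---|
| 10%/10% | 1.00 | 1.00 |
| 12%/8% | 1.02 | 1.02-1.03 |
| 15%/10% | 1.03 | 1.03 |
| 20%/10% | 1.06 | 1.05-1.06 |
| 30%/10% | 1.13 | 1.13-1.14 |
| 10%/20% | 0.95 | 0.94 |

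At a true HR of 0.5, 30%/10% gives 0.57 and 10%/20% gives 0.475. At 0.38, 20%/10% gives 0.41 and 30%/10% gives 0.43.

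**Do the weights help?** With withdrawal unrelated to prognosis, the weights left every simulated HR unchanged to three decimals. Next, withdrawal on ASA was tied to a prognostic covariate with 50% prevalence (assumed recurrence HR 2, withdrawal rate ratio 3). At 15%/5% and 30%/10%, weights fitted in PP3 balanced the arms at 48.5% and 46.9%, which is the PP3 mix and not the randomised 50%. The HR at a true value of 1 moved from 1.04 to 1.065 and from 1.09 to 1.15. Weights fitted in the FAP are close to 1, because arm was randomised, and they reproduce the unweighted result.

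**Do the remedies help?** Keeping leavers and censoring them at exit gives 0.995-1.006 at a true HR of 1 when exit is unrelated to prognosis. With prognostic exit on ASA only, plain censoring gives 0.971-0.986, so censoring weights on baseline covariates are needed as well. One weight per subject for PP membership, constant within arm because no covariate predicts exit in that run, leaves 1.029, 1.057 and 1.138 (15%/10%, 20%/10%, 30%/10%) unchanged.

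**Scale.** With 0.18 × 135 ≈ 24 events per arm, SE(log HR) ≈ √(2/24) = 0.29. An HR of 1.03 is then 0.1 SE from 1, 1.06 is 0.2 SE, and 1.13 is 0.4 SE.

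**The case against.** The primary endpoint and secondary endpoints 1-5 use the FAP (SAP Table 9). The per-protocol analyses are optional, exploratory and without p-values (8.3), and membership is fixed before unblinding (5.2). The SAP considered IPCW, gave its reasons and asks for limitations to be highlighted. The trial is double-blind, overall drop-out is put at 10%, and Protocol 10.5 puts excess gastrointestinal bleeding at around 0.1% per year. That figure does not bound all adverse-event withdrawal, but nothing in the documents supports 20%/10% or 30%/10%.

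Most of this stands and limits the weight of the point. It does not remove it. Blinded assignment prevents choice by arm but not selection on the outcome. Section 8.3 does not name that selection as a limitation, and a caveat cannot sit beside a contrary statement of the target. Of the reasons against IPCW, the undefined date of non-compliance does not apply to leavers, for whom 4.8.2 and 6.2.2 already use last-intake or end-of-study dates. Visit-specific non-compliance is a different matter from exit, and baseline-covariate weights need no time-dependent covariates. The first reason still holds for subjects who stay in the trial below 80% compliance.

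A reader might infer more than the documents support:
- That any difference in withdrawal between arms biases the HR. If all withdrawal is on day 0 (30%/10%), PP3 gives 0.992 against 0.994 in all subjects.
- That inflated 3-year risks will be reported. Table 13 plans curves on the FAP only, and Table 17 gives N, events, HR and CI for PP3.
- That the weights are fitted inside PP3. Section 8.3 says who receives them, not where the model is fitted. Neither reading meets the stated target.

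**Conclusion.** The point holds for the exploratory per-protocol analyses. Membership depends on the outcome, and the statement that the weights target the randomised population is wrong whatever the withdrawal rates turn out to be.

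The numerical bias is conditional. It needs withdrawal during follow-up that differs by arm, or exit tied to prognosis. It runs against the arm with more withdrawal, so it can also flatter aspirin. It is about 3% or less on the HR at arm gaps that fit the planned 10% overall, 5-6% at 20%/10%, and 13-14% at 30%/10%. Those splits are assumptions. No PP5 figure was computed; the point there rests on the identical structure of the rule. At the planned size these shifts are small beside sampling error, so a reading that the per-protocol result would show spurious harm, or that the trial's main conclusion is at risk, goes too far.

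**What to change.** 1. In SAP 8.3, delete or correct the statement that the weighting targets the randomised population, and name outcome-dependent selection among the limitations to be highlighted.
2. For subjects who leave without an event, keep their person-time and censor at the last-intake date if registered, otherwise at the end-of-study date. Use this as the per-protocol analysis or as a sensitivity analysis beside it, with time-to-exit censoring weights by arm on the baseline covariates already listed in 8.3. Do not use subject-level PP-membership weights, which leave this bias in place.
3. State how subjects who stay in the trial with under 80% compliance are handled. Otherwise step 2 would bring them in and silently drop the adherence rule.

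Cost: SAP wording and a modest programming change using dates already held in the eCRF. Downside: censoring at exit assumes that exit is non-informative given the baseline covariates.

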5.2.3 Safety population

The safety population (SP) consists of all randomized subjects who have received the IMP at least once.

5.3 Handling of trial sites

The ALASCCA trial includes subjects from Sweden, Denmark, Finland and Norway. In total, 33 hospitals have screened and recruited subjects, see Table 6 for the number of sites per country.

Table 6. Number of sites per country

Country	Number of sites
Sweden	24
Denmark	3
Finland	2
Norway	4
TOTAL	33

Due to the low number of randomized subjects per site, and, for the Nordic countries outside of Sweden, per country, no adjustment or stratification for site/country will be made in the analyses of study endpoints.

5.4 Missing data

The amount of missing data in the eCRF will likely be very small, due to the following efforts:

- Regular monitoring of all sites making sure the completeness of registration into the eCRF, and
- Regular contact between the central trial administration and local sites to request missing data.

If, despite the above efforts, baseline variables are still missing for some subjects, these subjects will be compared to subjects with non-missing baseline variables with regards to their non-missing characteristics. The number of missing values for each baseline characteristic will be clearly presented in the patient characteristics table, stratified by randomization and mutation group.

Only factors used in the randomization are adjusted for in endpoint analyses, and these variables have to be entered into the eCRF for a subject to be randomized. Hence, adjustment variables cannot be missing for any randomized subject. If there is a need to adjust for other variables in the analyses, and there are missing values, multiple imputation using chained equations will be used, using non-missing baseline variables to estimate the missing values, and using Rubin's rules to combine the imputed datasets. Fifty imputed datasets will be generated, and the seed will be set to 87228. Baseline characteristics that have a risk of containing missing values are platelet count, BMI, CEA, ASA score, tumor location in colon cancer, height from anal verge, neoadjuvant radiotherapy, neoadjuvant and adjuvant chemotherapy, emergency/elective surgery, specific type of surgery, and tumor differentiation. See Section 6.1 for a listing of baseline variables.

5.5 Multiple testing

No adjustment for multiple testing will be applied.

6 Summary of trial data

All data will be presented using descriptive statistics, stratified by randomized group and type of somatic alteration. Continuous variables will be summarized using median, interquartile range (IQR), minimum and maximum. Categorical variables will be summarized using the number and percentage of subjects. See Table 14 for a table template of how the baseline variables will be presented.

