### 10.13.3 Analysis of efficacy

The primary efficacy variable is TTR. Subjects who have not experienced loco-regional recurrence, distant metastases or death from colorectal cancer at time of 3- and 5- years will be censored at the time of the latest assessment. The log-rank test will be applied to test for difference in TTR between the treatment groups.

Kaplan-Meier estimates will be used for the estimation of median times to treatment failure and their confidence intervals. Secondary endpoints will be assessed using the log-rank test or

a Cox regression model, with time to treatment failure (relapse or death) as response variable and treatment group as factor.

All secondary variables will be presented descriptively with point estimate and 95% confidence intervals.

The data from the observation group will only be presented descriptively.

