4.2.2 Secondary objectives

- 1. To determine whether adjuvant treatment with 160 mg ASA once daily for 3 years compared with placebo can improve disease-free survival (DFS) in CRC patients with tumors harboring somatic alterations in the PIK3CA (exon 9 and/or 20) gene.
- 2. To determine whether adjuvant treatment with 160 mg ASA once daily for 3 years compared with placebo can improve TTR in CRC patients with tumors harboring somatic alterations in the PIK3CA (not exon 9 or 20), PIK3R1 and/or PTEN genes.
- 3. To determine whether adjuvant treatment with 160 mg ASA once daily for 3 years compared with placebo can improve DFS in CRC patients with tumors harboring somatic alterations in the PIK3CA (not exon 9 or 20), PIK3R1 and/or PTEN genes.
- 4. To determine whether adjuvant treatment with 160 mg ASA once daily for 3 years compared with placebo can improve overall survival (OS) in CRC patients with tumors harboring somatic alterations in the PIK3CA (exon 9 and/or 20) gene.
- 5. To determine whether adjuvant treatment with 160 mg ASA once daily for 3 years compared with placebo can improve OS in CRC patients with tumors harboring somatic alterations in the PIK3CA (not exon 9 or 20), PIK3R1 and/or PTEN genes.
- 6. To assess overall safety and tolerability.

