7.2 Safety interim analysis 2020

Data was extracted from the eCRF on January 17th, 2020, including subjects that were randomized up to and including October 21st, 2019, with follow-up up to and including January 17th, 2020. The safety report was sent to the SMC on March 5th, 2020.

The number of SAEs were summarized by randomized arm and visit. Fisher's exact test was used to test differences in frequencies of SAEs between randomized arms for each visit. Information on all SAEs were listed, see Table 8 for details. Similarly, the total number of AEs, and number of AEs per AE type (using the categories listed under "Type of SAE" in Table 8), were summarized by randomized arm and visit, and compared between arms for each visit using Fisher's exact test. The number of subjects with multiple AEs was also summarized by randomized arm, visit, and type of AE.

Table 8. SAE and AE details included in the 2018 and 2020 safety reports to the SMC

SAE variable	Categories
Visit number	4-9 (2018 report), 4-15 (2020 report)
SAE day	Day in relation to randomization date
Randomized arm	0/1 (not disclosing associated treatment)
Type of SAE	 Hematological
	 Cancer
	 Cardiovascular
	 CNS/Neurological
	 Dermatological
	- Endocrine
	 Eyes, ears, nose, throat
	 Gastrointestinal
	Urogenital
	Hormonal
	Immunological
	 Musculoskeletal
	Respiratory
	– Other
SAE description	 Leads to death
	 Is life threatening
	Other important medical event
	 Requires hospitalization for more than 24
	hours or extended medical care
	Causes permanent or significant
	invalidity/functional impairment
Intensity	– Mild
	- Moderate
T (185)	- Severe
Treatment modification	- Unchanged
	- Stopped
B "	Other, e.g., treatment pause
Result	- Restored
	- Under improvement
	Not Restored, with sequels
	Death

8 Analysis of trial endpoints

All tests and confidence intervals (CIs) will be two-sided. The significance level will be 5 %, and CIs will have 95 % confidence level. The endpoints and their respective variables and populations are summarized in Table 9.

Table 9. Specification of variables and populations for the primary endpoint or secondary endpoints 1-5 in the ALASCCA trial. Mutation A: PIK3CA exon 9 and 20 hotspot small mutations, Mutation B: other PIK3CA, PIK3R1 and PTEN non-silent small mutations and focal/homozygous deletion of PTEN.

Endpoint	Specification	Time variable	Event indicator	Population	Subgroup

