8.2 Secondary efficacy analyses

8.2.1 Secondary endpoints 1-5

The secondary endpoints 1-5 will be analyzed as described in Section 8.1. DFS and OS will be visualized using Kaplan-Meier estimates. For OS endpoints, the KM estimates for the net proportion or survival will be made at 5 years, and any analyses of OS endpoints will be performed earliest in 2026 when each randomized subject has a full 5-year follow-up. See Table 9 for specifications on endpoint variables, event indicators and subsets for secondary endpoints 1-5.

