8.3 Exploratory analyses

In addition to the primary efficacy analysis and the analyses of secondary endpoints, some or all of the exploratory analyses listed in Table 10 (3-year endpoints) and Table 11 (5-year endpoints) may also be performed. All exploratory endpoints on the FAP will be analyzed as described in Section 8.1, however, for analyses in only colon/rectum/left-sided/right-sided colon subjects, the strata will only be defined by stage. For analyses with subgroups based on adjuvant treatment, an interaction-term between randomization arm and a time-varying treatment indicator will be used considering that adjuvant treatment for some subjects starts post-randomization. In result tables for exploratory analyses, 95 % Cl's, unadjusted for multiple testing will be presented, but not p-values.

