Adjuvant chemotherapy in colon	Fluorouracil/capecitabin						
cancer	Fluorouracil/capecitabin + oxaliplatin						
	Other adjuvant chemotherapy						
	No adjuvant chemotherapy						
	Missing						
Adjuvant chemotherapy in rectal	Fluorouracil/capecitabin						
cancer	Fluorouracil/capecitabin + oxaliplatin						
	Other adjuvant chemotherapy						
	No adjuvant chemotherapy						
	Missing						

¹V600E ²Exons 12, 13, 59, 61, 117 and/or 146

Table 15. Table template for Table 2: Results from analysis of primary endpoint, and secondary endpoint 1-3. If the PHA is violated, one HR per time-interval (in addition to the overall HR).

Outcome	N (n events) in ASA arm	N (n events) in Placebo arm	HR ASA vs Placebo (95% CI; p)
TTR in PIK3CA exons 9/20			
DFS in PIK3CA exons 9/20			
TTR in PIK3CA (other exons), PIK3R1, PTEN			
DFS in PIK3CA (other exons), PIK3R1, PTEN			

Table 16. Table template for Table 3: Results from analysis of secondary endpoints 4-5.

Outcome	N (n events) in ASA arm	N (n events) in Placebo arm	HR ASA vs Placebo (95% CI; p)
OS in PIK3CA exons 9/20			
OS in PIK3CA (other exons), PIK3R1, PTEN			

Table 17. Table template for Table 4: Results from analysis of exploratory endpoints.

Outcome	Subgroup	N (n events) in ASA arm	N (n events) in Placebo arm	HR ASA vs Placebo (95% CI)
TTR	PIK3CA exons 9/20 (PP3 population)			
TTR	PIK3CA (other exons), PIK3R1, PTEN (PP3 population)			

Table 18. Table template for Table 5: Number of SAEs per randomized arm.

		Randomiz	ed to ASA	Randomized	to Placebo
		Number of SAEs (%)	N subjects in SP	Number of SAEs (%)	N subjects in SP
Total					
Time from randomization (months)	Median (IQR, min- max)				
Type of SAE	Hematological				
• •	Cancer				
	Cardiovascular				
	CNS/Neurological				
	Dermatological				
İ	Endocrine				

		Randomize	Randomized to ASA		to Placebo
		Number of SAEs (%)	N subjects in SP	Number of SAEs (%)	N subjects in SP
	Eyes, ears, nose, throat				
	Gastrointestinal				
	Urogenital				
	Immunological				
	Musculoskeletal				
	Respiratory				
	Other				
SAE description	Leads to death				
	Is life threatening				
	Other important				
	medical event				
	Requires				
	hospitalization for more than 24 hours or				
	extended medical care				
	Causes permanent or significant invalidity/functional				
	impairment				
Intensity	Mild				
•	Moderate				
	Severe				
Treatment modification	Unchanged				
	Stopped				
	Other, e.g. treatment				
	pause				
Result	Restored				
	Under improvement				

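### The SAP tests secondary endpoints 1-5 each at two-sided 5% with p-values and no multiplicity control, while the protocol says secondary variables are presented descriptively

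*SAP*

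**What the plan says.** - **SAP 5.5, Multiple testing:** "No adjustment for multiple testing will be applied".
- **SAP Section 8, opening paragraph:** "All tests and confidence intervals (CIs) will be two-sided", and "The significance level will be 5 %, and CIs will have 95 % confidence level".
- **SAP 8.2.1:** "The secondary endpoints 1-5 will be analyzed as described in Section 8.1". Section 8.1 is a stratified Cox model with a two-sided p-value for the null hypothesis of no treatment effect.
- **SAP Table 12** lists a p-value column for the results of secondary endpoints 1-3 and 4-5. **Templates 15 and 16** carry the column "HR ASA vs Placebo (95% CI; p"). Template 15 shows the primary and secondaries 1-3 in one table under that column.
- **SAP 4.2.2** words secondary objectives 1-5 like the primary one, for example "To determine whether adjuvant treatment with 160 mg ASA once daily for 3 years compared with placebo can improve overall survival (OS").
- **SAP 8.3**, on exploratory analyses, says the confidence intervals "unadjusted for multiple testing will be presented, but not p-values".
- **Protocol 10.13.3** (the synopsis has the same sentence): "All secondary variables will be presented descriptively with point estimate and 95% confidence intervals". The same section also says secondary endpoints are assessed by log-rank test or Cox model.

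**The concern.** The SAP numbers its secondary endpoints (DFS A, TTR B, DFS B, OS A, OS B), but nothing makes the numbers a testing order or ties a secondary test to the primary result. Five p-values will therefore appear in the primary's format, each judged at 5%, and the reader is not told how to weigh them. The two documents do not settle whether these tests are confirmatory or descriptive. SAP 8.3 omits p-values for exploratory analyses that are no less adjusted than the secondaries.

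Three of the five secondary tests are in Mutation B. SAP 4.9.6 analyses a subject with both alteration types as A, so the two groups share no subjects and B carries its own chance of a false positive. Protocol Section 8 (Introduction) calls the role of *PIK3R1* and *PTEN* mutations in ASA's effect unknown and bases power on exon 9 and 20 only. An isolated nominal p<0.05 in Mutation B is thus the result most open to over-reading.

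**Working it through.** **Stated figure.** Neither document gives an error rate for the secondary family, so there is none to reproduce. The one stated design calculation (SAP 4.5.2) assigns two-sided 5% to the primary: 18% against 0.38 × 18% = 6.84%. A two-proportion formula gives 136 per arm for 80% power (stated 135), 79.7% power at 135, and 135/0.9 = 150. It reproduces, and it covers the primary only.

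**Inputs from the documents.** Five secondary tests, each at two-sided 0.05: two in Mutation A (DFS, OS) and three in Mutation B (TTR, DFS, OS). A and B are disjoint, so their test statistics are taken as independent.

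**Assumption.** Correlations between TTR, DFS and OS statistics within a group are not given. They must be positive, because TTR events also count for DFS and deaths count for both DFS and OS. They are varied below. All figures assume no effect of ASA on any of the endpoints concerned.

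**Step 1: bounds by formula.**
- Tests independent, any p<0.05: 1 − 0.95^5 = 0.226.
- Tests perfectly correlated within each group (in effect two tests): 1 − 0.95^2 = 0.0975.
- Counting only rejections that favour ASA (0.025 per test): 1 − 0.975^5 = 0.119, and 1 − 0.975^2 = 0.049.

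**Step 2: intermediate correlations.** Two million draws of multivariate normal z-statistics, rejecting at |z| > 1.96. A favourable rejection is in ASA's direction only.

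| Within-group correlation | Any of five, two-sided | Any of five, favouring ASA | Secondaries 1-3, two-sided | Secondaries 1-3, favouring ASA |
|---|---|---|---|---|
| 0 | 0.226 | 0.119 | 0.143 | 0.073 |
| 0.5 | 0.204 | 0.105 | 0.136 | 0.069 |
| TTR-DFS 0.8, DFS-OS 0.7, TTR-OS 0.6 | 0.183 | 0.094 | 0.124 | 0.063 |
| 0.9 | 0.148 | 0.075 | 0.117 | 0.059 |

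**Step 3: related quantities at 0.8/0.7/0.6.**
- At least one false positive in Mutation B: 0.108 two-sided, 0.054 favouring ASA.
- Primary not significant but at least one secondary significant: 0.154 two-sided. Counting only results favouring ASA for both: 0.080.

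**Step 4: patient-level check.** Log-rank tests were simulated with 150 per arm in each group, TTR and DFS to 3 years and OS to 5 years, 6,000 runs per scenario. Assumed inputs were 3-year recurrence 12-18%, other cancer 2-8%, non-CRC death 2-8%, and an annual death hazard after recurrence of 0.20-0.35. Over five scenarios the two-sided rate was 17.4-19.6% for all five tests and 11.3-13.2% for secondaries 1-3. Simulated correlations were 0.71-0.91 (TTR-DFS), 0.55-0.69 (DFS-OS) and 0.41-0.66 (TTR-OS), inside the range of Step 2.

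**Step 5: timing.** SAP 5.1 places secondaries 1-3 with the primary in 2024 and OS from August 2026. The five-test rate applies only once both OS tests are done.

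**The case against.** The strongest reply is that the trial has one primary endpoint in one population with one test, and that test keeps its 5%. The interim analyses cover safety only. Non-adjustment is declared in advance, and whether secondaries behind a single primary need family-wise control is partly convention. All of that stands, and it limits the weight of the point. Declaring non-adjustment still does not say how five p-values in the primary's format are to be read.

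Four stronger readings are tempting, and the documents do not support them:

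- **That the plan nowhere calls the secondaries descriptive.** This is true of the SAP only; the protocol says so twice.
- **That the SAP turned descriptive endpoints into confirmatory ones.** The protocol already names log-rank or Cox for them and already words its DFS and TTR secondary objectives as determining an improvement. Only its OS objective is worded as a comparison. The protocol is itself mixed.
- **That a significant secondary licenses a claim if the primary fails.** Neither document contains such a rule. The gap is that nothing rules it out.
- **That SAP 8.3 withholds exploratory p-values because they are unadjusted.** It gives no reason. Only the difference in treatment is on the page.

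It is also fair that a two-sided rate overstates the risk of a false claim of benefit, since about half of the false positives would point towards placebo. The favourable-only figures answer this.

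**Conclusion.** The point holds as a mismatch between SAP and protocol, with no control of the secondary family. It does not affect the validity of the primary analysis.

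If ASA affects no secondary endpoint, the chance of at least one nominal p<0.05 among the five is about 15-23% for within-group correlations of 0.9 to 0, with a lower bound of about 10%. The chance of a false result in ASA's favour is about 7.5-12%, with a lower bound of about 5%. At the 3-year analysis the two-sided figure is about 12-14%.

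A reader might infer one firm rate of 18-20%. The documents do not support that: they give no correlations, and the figure needs no effect on any secondary endpoint and completion of the 2026 OS tests. The two-sided excess over 5% does not depend on the correlation chosen. The 5% itself is a per-test level, which the SAP never presents as a family-wise rate.

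**What to change.** 1. **SAP 5.5:** state that only the primary endpoint is a confirmatory test, at two-sided 5%. State that secondary endpoints 1-5 are descriptive, reported as HR with 95% CI unadjusted for multiplicity, and not used for claims of effect.
2. **SAP 8.2.1:** keep the Section 8.1 model for estimation, but exempt secondaries 1-5 from its hypothesis test and p-value.
3. **Tables:** remove the p-value for secondary endpoints from Table 12, from the secondary rows of Table 15 and from Table 16. Changing the templates alone would leave Table 12 and 8.2.1 still asking for it.

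This brings the SAP into line with Protocol 10.13.3 and with SAP 8.3. It changes wording only, not data, sample size or the primary test. SAP 1.1 was itself a revision made before unblinding, and the same route fits. The cost is that no secondary result can be claimed as statistically significant.

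A pre-specified testing order starting with the primary is an optional alternative and would hold the family-wise rate at 5%. The existing numbering should not be adopted for it without thought: it places OS in Mutation A, the primary population, behind two Mutation B tests, and places every Mutation B test behind DFS in A. Nothing in the SAP says the numbering reflects priority.
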